## **1.4. Clinical Experience**

### **1.4.1. N6LS**

As of August 4, 2021, 27 subjects have enrolled into Groups 1-8. A total of 22 out of 23 subjects enrolled in Groups 1-6 received N6LS study product administrations and completed the protocol. One subject in Group 2 terminated the study after enrolling but prior to product administration. The N6LS product has been administered to 14 subjects by IV infusion and 12 subjects by SC injection. Unsolicited AEs were reported by 16/26 (62%) subjects that received N6LS, with the most frequent events of upper respiratory tract infection (URTI) reported by 6 subjects (23%) and diarrhea reported by 4 subjects (15%). All unsolicited events were mild or moderate in

severity except for one grade 3 diarrhea that began 4 days after administration, spontaneously resolved 2 days later, and was determined to be possibly related to N6LS.

Solicited systemic symptoms were reported in 4/14 (29%) subjects following IV administration and 3/12 (25%) subjects following SC administration. Symptoms reported after IV administration included 4 events of mild headache, 1 mild event each of malaise, chills, and nausea. Symptoms reported after SC administration included 1 mild event each of malaise, myalgia, headache, and nausea. No fevers occurred after IV or SC administration.

Solicited local symptoms reported included moderate bruising (1/14 subjects, 7%) following IV administration. Solicited local symptoms after SC administration included mild pain/tenderness (9/12 subjects, 75%), mild to moderate swelling (4/12 subjects, 33%), mild to severe redness 6/12 subjects, 50%), and mild pruritus (3/12 subjects, 25%).

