SC administration of CD4-binding site mAbs has been well tolerated in adults and infants. Most study participants had either no local reactogenicity or local symptoms limited to injection site pain and/or tenderness, redness, and mild localized pruritus (itchiness). Most local symptoms resolve within the first days after product administration. In some cases moderate to severe erythema at the injection site have lasted up to six weeks post product administration before resolving without clinical sequelae.

Preliminary N6LS PK data showed the maximum serum concentrations (Cmax) occurred within the first few hours after IV administration, and approximately 6 days following SC administration. The mean ( $\pm$ SD) Cmax values after a single administration of N6LS were  $28\pm10$   $\mu$ g/mL for the 5 mg/kg SC dose,  $101\pm23$   $\mu$ g/mL for the 5 mg/kg IV dose,  $589\pm236$   $\mu$ g/mL for the 20 mg/kg IV dose, and  $1717\pm51$   $\mu$ g/mL for the 40 mg/kg IV dose.

Preliminary mean ( $\pm$ SD)  $C_{28D}$  serum concentrations after the first administration of N6LS were  $15\pm6.1$   $\mu$ g/mL,  $32\pm2.3$   $\mu$ g/mL,  $96\pm25.4$   $\mu$ g/mL, and  $43\pm1.3$   $\mu$ g/mL for the 5 mg/kg SC, 5mg/kg IV, 20 mg/kg IV, and 40 mg/kg IV doses, respectively.

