## **6.2. Sample Size Considerations**

Although the study is primarily descriptive, the primary goal is to identify safety concerns associated with different N6LS dosages in group sizes ranging from 3 to 5 subjects. For a group size of 3 subjects, there is a 90% chance of observing at least 1 SAE if the true event rate is  $\geq 0.536$  and a 90% chance of observing no SAE if the true event rate is  $\leq 0.034$ . For a group size of 5 subjects, there is a 90% chance of observing at least SAE if the true rate is  $\geq 0.37$  and a 90% chance of observing no event if the true rate is  $\leq 0.02$ . The probabilities of observing 0 and 1 or more event are presented in Table 3 for a range of possible true event rates. These calculations provide a complete picture of the sensitivity of this study design to identify potential safety problems with the study agent. For example, within the group of size n=3, if the true event rate is 0.01, then there is a probability of 0.97 to observe no event and a probability of 0.03 to observe at least 1 event; while, within the group of size n=5, if the true event rate is 0.01, then there is a probability of 0.951 to observe no event and a probability of 0.05 to observe more than 1 event.

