**Table 4: 95% Confidence Intervals of the True Rate for All Possible Number of Observed Events within a Dose Group**

Group Size, N=3 95% Confidence Interval			Group Size, N=5 95% Confidence Interval		
Observed Rate	Lower Bound	Upper Bound	Observed Rate	Lower Bound	Upper Bound
0/3	0	0.708	0/5	0	0.522
1/3	0.008	0.906	1/5	0.005	0.716
2/3	0.094	0.992	2/5	0.053	0.853
3/3	0.292	1	3/5	0.147	0.947
			4/5	0.284	0.995
			5/5	0.478	1

Table 3 and Table 4 also apply to the secondary and exploratory objectives.

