#### **6.3.5. Pharmacokinetics Analysis**

Blood samples for PK evaluations will be collected at time-points defined in the Schedule of Evaluations (Appendix I).

**Individual Subject Pharmacokinetic Analysis:** A non-compartmental PK analysis will be performed using Phoenix 7.0 (CertaraR) or a similar program on the N6LS concentration data generated from each subject. Calculated PK parameters for IV Groups 1, 3, 4, and 6 will include: area-under-the-curve (AUC), maximum concentration ( $C_{max}$ ), time to  $C_{max}$  ( $T_{max}$ ), clearance (CL), volume of distribution ( $Vd_z$ ), terminal elimination rate constant ( $\lambda_z$ ) and the terminal half-life ( $T_{1/2}$ ). For Groups 2, 5, 7 and 8, the PK parameters will include AUC,  $C_{max}$ ,  $T_{max}$ , apparent clearance (CL/F), apparent volume of distribution ( $Vd_z/F$ ),  $\lambda_z$  and  $T_{1/2}$ .  $C_{max}$  and  $T_{max}$  will be taken directly from the observed concentration-time data. The terminal slope,  $\lambda_z$ , will be determined from the log-linear portion of the curve and the  $T_{1/2}$  calculated as  $0.693/\lambda_z$ . AUC will be determined using the linear trapezoidal method through the Week 24 PK sample for single dose groups (1-4, 7 and 8) and through Week 48 for multiple dose groups (5 and 6) or through the last PK sample with a concentration above the quantitative limit. The AUC over the

first 12 weeks following the first dose ( $AUC_{0-WK12}$ ) will be determined for all dose groups. If the final sample ( $C_{last}$ ) has a measurable N6LS concentration, the remaining AUC after the final concentration ( $AUC_{last-inf}$ ) will be estimated as  $C_{last}/\lambda_z$ . Data will be summarized by dose group and overall for IV administration groups for CL, Vd and  $T_{1/2}$ . For Groups 5 and 6, potential accumulation will be assessed as the ratios of the  $AUC_{0-WK12}$  and  $C_{max}$  for the first and the third doses. The potential for non-linearity PKs among IV groups will be determined by comparing the dose-adjusted ratios for  $C_{max}$  and  $AUC_{0-WK12}$  between IV groups. Additional compartmental analysis will be performed as warranted by the data.

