**Population Pharmacokinetic Analyses:** Population PK analyses will be performed on the N6LS PK data following IV and SC administration to determine compartmental PK parameters with the PK program NONMEM version 7.3 or later (ICONR). Based on prior PK studies of bNAbs, a two compartment model will be used to analyze the N6LS PK data. The population analysis will generate estimates for initial and final volumes of distribution ( $Vd_1$  and  $Vd_2$ ), inter-compartmental clearance (Q), CL and bioavailability (F). Individual subjects' empiric Bayesian PK parameter estimates will be generated using the NONMEM posthoc subroutine. Given the small subject numbers, the population PK analysis will include a limited exploratory covariate analysis to assess dosing and clinical factors as fixed effects associated with N6LS PK parameters. The three factors that will be evaluated are dose level (5 vs 20 vs 40 mg/kg) on CL  $Vd_1$ ,  $Vd_2$  and F; repeat dosing CL  $Vd_1$ ,  $Vd_2$ , and F; and EPD co-administration on SC F and absorption rate.

The longer compartmental half-life,  $T_{1/2\beta}$  will be determined from CL,  $Vd_1$ ,  $Vd_2$  and Q using standard PK equations. Final model selection will be based on changes in the objective function and graphically by goodness of fit plots. The final population PK model will be assessed using bootstrap analysis. N6LS dosing strategies and their ability to achieve and maintain target N6LS concentrations will be performed using the final population PK model and Monte Carlo simulations with at least 5000 replicates.

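### IV dose-linearity is to be judged from dose-adjusted ratios between groups of 3 to 5 subjects with no interval or model; add a power-model slope and ratio with 95% CIs

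*Combined protocol and SAP*

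**What the plan says.** Section 6.3.5 plans a non-compartmental analysis for each subject. On linearity it says: "The potential for non-linearity PKs among IV groups will be determined by comparing the dose-adjusted ratios for" Cmax and AUC0-WK12 between IV groups. It names no interval, model, threshold or decision rule. It does not say whether Groups 3 and 6, both 20 mg/kg IV, are combined, or which dose supplies the Group 6 Cmax.

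On the disposition parameters the same section says: "Data will be summarized by dose group and overall for IV administration groups for CL, Vd and" half-life. Both a by-dose and an overall IV summary are therefore planned, and nothing ties the overall figure to the linearity result.

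The population PK paragraph of 6.3.5 adds a covariate analysis: "The three factors that will be evaluated are dose level (5 vs 20 vs 40 mg/kg) on CL", the two volumes and bioavailability. It describes this as limited and exploratory. "Final model selection will be based on changes in the objective function and graphically by goodness of fit plots", and the final model is then bootstrapped.

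The only precision statement that reaches PK is the line under Table 4: "Table 3 and Table 4 also apply to the secondary and exploratory objectives". Tables 3 and 4 are binomial.

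**The concern.** A ratio of dose-adjusted means from a handful of subjects can stray well from 1 by chance. Without an interval, the reader cannot tell whether a ratio of, say, 1.5 is evidence of non-linearity or ordinary variation, and two readers could reach opposite conclusions from the same table. The binomial tables do not help, because they give no precision for a ratio of PK means.

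The question is a live one. Section 1.4.1 reports preliminary IV Cmax values that rise faster than dose. Section 6.3.6 says interim PK results will inform dose levels in later studies. An overall IV value for CL, Vd or half-life could be quoted on its own, and 8 of the 14 IV subjects (57%) are at 20 mg/kg.

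**Working it through.** **The plan's own figures.** Section 6.2 says: "For a group size of 3 subjects, there is a 90% chance of observing at least 1 SAE if the true event rate is" at least 0.536. Check: 1 − 0.1^(1/3) = 0.536, and 1 − 0.9^(1/3) = 0.0345 (stated 0.034). For n = 5 the results are 0.369 and 0.0209 (stated 0.37 and 0.02). Tables 3 and 4 also reproduce. No figure for PK precision is stated, so there is none to reproduce.

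**Subjects.** Table 1 gives 3 (Group 1, 5 mg/kg), 3 + 5 (Groups 3 and 6, 20 mg/kg) and 3 (Group 4, 40 mg/kg), which makes 14. Section 1.4.1 agrees: "The N6LS product has been administered to 14 subjects by IV infusion and 12 subjects by SC injection".

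**Precision of the 40-versus-5 ratio.** The CV is an assumption, shown at 30% and 40%. With s = √ln(1 + CV²), s = 0.294 or 0.385. For the power model x = ln(dose) with n = 3/8/3, so Sxx = 6.90, and ln(40/5) = 2.079.

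| Method | 95% CI factor | CV 30% | CV 40% |
|---|---|---|---|
| 3 vs 3 alone (4 df) | exp(2.776·s·√(2/3)) | 1.95 | 2.39 |
| 3 vs 3, variance pooled over 14 (11 df) | exp(2.201·s·√(2/3)) | 1.69 | 2.00 |
| Power model, all 14 (12 df) | exp(2.179·s·2.079/√6.90) | 1.66 | 1.94 |

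Most of the gain comes from estimating the variance on all 14 subjects. The regression itself adds little.

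**Preliminary Cmax (Section 1.4.1).** The means are 101, 589 and 1717 µg/mL, the last of these "for the 40 mg/kg IV dose".
- Per mg/kg: 101/5 = 20.2; 589/20 = 29.5; 1717/40 = 42.9. The 40-versus-5 ratio is 42.9/20.2 = 2.13.
- Slope of ln(mean Cmax) on ln(dose), weighted 3/8/3: 1.34, where 1 is proportional. The 95% half-width is 2.179·s/√6.90.
- Assumed CV 30%: 1.10–1.58. CV 40%: 1.02–1.66. CV 50%: 0.95–1.73.
- The n behind the 20 mg/kg value is not stated. If it is 3, the slope is 1.35, and the lower limit at CV 40% is 0.998.
- With the reported SDs in place of an assumed CV (log-normal, n = 3/8/3), the slope is 1.34 (95% CI 1.07–1.61). Those SDs imply very unequal CVs: 23/101 = 23%, 236/589 = 40% and 51/1717 = 3%.

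**Preliminary day-28 concentration (same section).** The means are 32, 96 and 43 µg/mL.
- Per mg/kg: 32/5 = 6.4; 96/20 = 4.8; 43/40 = 1.1.
- The trend is opposite to that of Cmax, and the 40 mg/kg value is below the 20 mg/kg value in absolute terms.
- Day-28 over Cmax: 32/101 = 0.32; 96/589 = 0.16; 43/1717 = 0.025.

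**The case against.** The other side has several good points. The study is primarily descriptive and PK is a secondary objective; no proportionality claim or margin rests on these ratios. The population model tests dose level on clearance and volumes, and that model, not the overall non-compartmental summary, drives the dosing simulations. All of this stands. It limits the weight of the point, but it does not supply the missing interval, and the covariate check is itself exploratory with no stated criterion.

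Four stronger readings are tempting, and the documents do not support them.

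- **That the 20 mg/kg subjects are left out.** They are not: the comparison is between IV groups, and Groups 3 and 6 are among them.
- **That CL, Vd and half-life are simply pooled over dose.** The same sentence requires them by dose group as well, so the overall figure is additional.
- **That the Cmax trend shows a two-fold difference in Vd, or dose-dependent CL or half-life.** Dose over end-of-infusion Cmax mainly reflects initial volume, whereas the planned Vd is the terminal-phase Vd_z. No preliminary AUC, CL, Vd_z or half-life is given, the day-28 values run the other way, and the slope interval includes 1 at a CV of 50%.
- **That pooling should be allowed only if the slope interval includes 1.** That treats failure to reject as evidence of linearity, so noisier data would make pooling easier. At CV 40% the half-width is 0.32, so a slope of 1.3 would pass, although it means an 8^0.3 = 1.9-fold departure over the dose range.

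**Conclusion.** The gap is real but limited. The non-compartmental linearity comparison has no interval or model, and at these group sizes its main contrast is uncertain by a factor of about 1.7 to 2.4 either way, for assumed CVs of 30–40% and depending on how the variance is estimated. A power model on all 14 IV subjects brings this to 1.66–1.94 and, more importantly, puts an interval on the result.

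The preliminary Cmax values suggest a more than proportional rise (slope about 1.34), but whether 1 is excluded depends on the assumed CV and on an unstated n. The preliminary Cmax and day-28 values should be verified before either is interpreted. No conclusion about Vd_z, CL or half-life can be drawn from them yet. The calculations assume log-normal data with a common CV and Groups 3 and 6 combined; the assumed-CV slope uses logs of arithmetic means.

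**What to change.** In Section 6.3.5:

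1. Regress ln(Cmax) and ln(AUC0-WK12), both after the first dose, on ln(dose) across Groups 1, 3, 4 and 6, stating that Groups 3 and 6 are combined at 20 mg/kg. Report the slope and the 40-versus-5 dose-adjusted geometric mean ratio with 95% CIs. Keep the pairwise dose-adjusted ratios as a descriptive display.
2. Make the by-dose CL, Vd and half-life the main summary. Show the overall IV figure beside the slope intervals and the population PK dose-covariate result, and do not make it depend on whether the slope interval includes 1.

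In Section 1.4.1, verify the preliminary Cmax and day-28 values and state the n behind each.

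The cost is one regression per parameter and a few sentences, with no new data. The small downside is that the power model assumes a straight line on the log-log scale, which three dose levels can check only roughly; the pairwise display helps there.

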### 6.3.6. Interim Analyses

Preliminary PK analyses may be done once per dose level as the data for each dose level is obtained. This may be performed before a dose group's PK data is complete and may only generate a subset of the final PK parameters. The interim analyses will be used to inform decisions about the dose levels to be administered in future studies with N6LS.

## 7. PHARMACY PROCEDURES

The dose groups and N6LS dosing schedule are shown in Table 1. Refer to the N6LS IB for further information about N6LS (VRC-HIVMAB091-00-AB) administered in the absence and presence of rHuPH20.

### 7.1. Study Product and Administration Regimen

N6LS (VRC-HIVMAB091-00-AB) is a clear, colorless to yellow liquid, sterile aqueous buffered solution that is essentially free of visible particles and is filled into 10 mL single-dose vials. Each vial contains a  $6.25 \pm 0.10$  mL volume of N6LS at a concentration of  $100 \pm 10$  mg/mL in formulation buffer composed of 10 mM Sodium Citrate, 50 mM Sodium Chloride, 150 mM Arginine-HCl, and 0.002% Polysorbate-80 (PS-80) at pH 6.5. Vials have a nominal fill volume of 6.25 mL to enable withdrawal up to 6.0 mL.

In calculating the dose to administer and number of vials to thaw, it should be assumed that the concentration is 100 mg/mL and that a volume of at least 6 mL can be withdrawn from a vial. In this trial, dose is limited or established based on subject weight. *For example*, for a subject weighing 115 kg (the upper limit per protocol eligibility) who receives the 40 mg/kg dose, the N6LS amount needed is calculated as follows:  $115 \text{ kg} \times 40 \text{ mg/kg} = 4600 \text{ mg}$  of N6LS, which corresponds to 46 mL of the 100 mg/mL solution. Since each product vial contains at least 6 mL, 8 vials will be needed for the dose preparation for this subject.

Preparation of N6LS for IV administration will require a 100 mL bag of 0.9% sodium chloride, United States Pharmacopeia (USP) (normal saline) and a weight-based amount of N6LS, as described in the IB. Preparation of N6LS (with and without rHuPH20) for SC administration will not require any diluent.

There are 6 different schedules in the study described in Appendix I.

### 7.2. N6LS (VRC-HIVMAB091-00-AB) Vialed Product

The N6LS product label designates the long-term storage temperature as -35°C to -15°C. Clinical site storage in a qualified, continuously monitored, temperature-controlled freezer with temperature excursions between -45°C to -10°C is acceptable.

Following thaw, N6LS vials may be stored for up to 24 hours at 15°C to 27°C and/or up to 4 weeks at 2°C to 8°C. Product may not be stored in direct sunlight. If stored at 2°C to 8°C, vials must be equilibrated to 15°C to 27°C for a minimum of 60 minutes and may be held at this temperature for up to 8 hours prior to product preparation.

### 7.3. EDP Vialed Product

EDP is supplied as a sterile solution at a concentration of 1 mg/mL in 2 mL single-use glass vial containing 0.5 mg rHuPH20 (~110,000 U/mL). EDP should be stored as labeled, either at -20°C  $\pm 5^\circ\text{C}$  or  $5^\circ\text{C} \pm 3^\circ\text{C}$  and protected from light. Vials of EDP for injection can be removed from frozen storage and placed in the refrigerator at 2°C to 8°C for thawing (1 to 2 hours), or room temperature (20°C to 25°C) for 10 to 30 minutes. Once thawed, vials of EDP may be kept at room temperature (20°C to 25°C) for up to 24 hours before use and protected from bright light and direct sunlight.

## **7.4. Temperature Excursions**

The site pharmacist must promptly report any storage temperature excursions outside of the normal allowance for the investigational products to the IND Sponsor. In the case of storage or shipping/handling temperature excursions outside of the normal allowance for the storage device, the following procedure is to be followed:

1. Quarantine the affected product in a separate area. If the excursion results in thawed material, it must not be refrozen. Thawed vials must be quarantined at  $5^{\circ}\text{C} \pm 3^{\circ}\text{C}$ .
2. Report the excursion to the IND sponsor's authorized representative (SAR) or designee, any other parties required by site procedures, and via email to [[contact]](mailto:[contact]). Do not use until the IND SAR or designee informs the site pharmacist whether continued clinical use of the product is acceptable.
3. Inquiries sent to [[contact]](mailto:[contact]). will prompt an automatic email reply to the notifier that includes the Clinical Excursion Reporting Form (CERF) as an attachment.
4. Fill out the CERF as completely as possible, either electronically or manually.
5. Email the completed form and relevant attachments (e.g., temperature charts) to [[contact]](mailto:[contact]), replying to the previous email.
6. After receipt and evaluation of the reported information, the Sponsor or manufacturer's designee will notify the site pharmacist whether continued clinical use of the product is acceptable.

## **7.5. Preparation of Study Product(s) (N6LS $\pm$ rHuPH20) for Administration**

This section describes how the site pharmacist will prepare the study products for administration and how the clinician will administer each product. Clinician instructions on how to select an administration site are in Section 4.2.3.

N6LS is a highly concentrated protein solution and may develop white, opaque to translucent particles after thawing. When particles are observed, they may disappear after a few hours at  $15^{\circ}\text{C}$  to  $27^{\circ}\text{C}$  or storage at  $2^{\circ}\text{C}$  to  $8^{\circ}\text{C}$ .

The following instructions apply to thawing N6LS:

1. Thaw vial(s) for a minimum of 90 minutes at  $15^{\circ}\text{C}$  to  $27^{\circ}\text{C}$  after removing from the freezer. (DO NOT move vials directly from the freezer to storage at  $2^{\circ}\text{C}$  to  $8^{\circ}\text{C}$ .)
2. Keep the material at  $15^{\circ}\text{C}$  to  $27^{\circ}\text{C}$  during the entire preparation period until use, up to the maximum storage times described in Section 7.2.
3. Prior to preparation for administration, vials should be swirled for 30 seconds with sufficient force to resuspend any visible particles, yet avoiding foaming. DO NOT SHAKE THE VIALS.
  - a. Visually inspect the vials; if 10 or fewer visible particles are present, the vial may be used for product preparation.

- b. If more than 10 particles are observed, return the vials to 2°C to 8°C storage. If the particles dissolve or if 10 or fewer visible particles are present within the maximum storage times described in Section 7.2, the vials may be used for product preparation.
  - c. Refrigerated product must be equilibrated at 15°C to 27°C for a minimum of 60 minutes before preparation and must be used within 8 hours of any subsequent return to 15°C to 27°C.
4. If the thawed material is not administered within 24 hours of thaw, follow the storage information provided in Section 7.2.

Preparation is to be done using aseptic technique, in a laminar flow biosafety cabinet. Assure that only the required vials are present in the preparation unit during dilution, and medication labels are strictly segregated to avoid mix-ups. More information on product preparation can be found in the IB.

#### **7.5.1. N6LS: Preparation for IV Administration**

For each IV infusion order, the subject's weight, dose level, and study group code will be included in the pharmacy order. To prepare an IV infusion, the pharmacist will: 1) fill an empty sterile bag with 100 mL of normal saline or (if commercially available) obtain a pre-filled 100 mL bag of normal saline, 2) calculate the total milligrams of N6LS needed, 3) retrieve the minimum number of thawed vials required to prepare the full dose, 4) withdraw the necessary amount of N6LS, 5) add this volume to the sterile bag using good pharmacy practices to maintain sterility, and 6) immediately remove all air remaining in the bag. Prepared IV bags should contain 10 particles or fewer to proceed with the administration to subjects.

An in-line filter infusion set must be used for IV product administrations and **MUST** comply with the following specifications: 1.2 micron PES (polyethersulfone) filter membrane, DEHP-free, latex-free (equivalent to Braun #473994 filter extension set). When the in-line filter is added to the tubing, the administration set must then be primed. At the end of product administration, the IV administration set must be flushed with about 30 mL (or appropriate volume) of normal saline.

The study product solution will typically be administered IV over about 15-30 minutes using a volumetric pump. The total time needed to administer the dose may be longer based on factors such as subject tolerance. The rate of infusion may range from 10-20 mg/kg/hr at the lowest dose level to 80-160 mg/kg/hr at the highest dose level. The mL/hr infusion rate may vary based on the total volume needed to administer a full dose. An infusion time greater than 30 minutes is permitted.

